1.3. Efficacy data

1.3.1. Primary Endpoints

Safety and tolerability based on avelumab related adverse events leading to permanent or transient discontinuation of avelumab

Treatment related adverse events of special interest will include those of autoimmune origin (irAE).

The adverse events will be graded according to the National Cancer Institute Common Terminology Criteria for Adverse Events, version 5.0

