##### **Exploratory objectives:**

To explore biomarkers that could predict treatment response to avelumab such as: the tumor immunoscore, presence and extent of PD-L1 expression on tumor cells and microglia/macrophages within the tumor

To correlate the OS and PFS in relation to the baseline value and the change from baseline to week 52 visit and every 52 weeks /or end of study visit (depending on whether the latter occurs before or after week 260) neurocognitive function as measured by the evoked potential P300 (normal), the baseline corticosteroid dose, the total cumulative corticosteroid dose over the whole study duration, the total cumulative temozolomide dose per BSA since diagnosis and the presence and severity of immune related adverse events (irAE's).

To assess and compare above mentioned biomarkers in tissue samples from patients with second surgical resection ie treatment failures.

To assess in this GBM population the duration of pseudoprogression and the lagtime needed for immunotherapy to become effective.

**Study Design:** This is a single center, phase 2, open-ended, open label, add-on, single dose study in patients receiving standard therapy for newly diagnosed GBM with

a projected duration of 5 years (260 weeks). In total 30 patients who meet the entry criteria will be entered into the study within 3 weeks of finishing their last day of combined radiotherapy/temozolamide. Avelumab will be initiated concurrently with the initiation of the first 5 days, monthly cycle of temozolamide and continued until the occurrence of a termination event defined as one of the following: 1) clinical evidence of neurological deterioration resulting in an ECOG score of at least 3 or more, unexplained by other comorbidities, unchanged by an increase in corticosteroid dose and sustained for at least two weeks or 2) treatment emergent adverse event (TEAE) of grade 3 or more or 3) withdrawal of patient consent.

A local pathology report will constitute adequate documentation of histology for study inclusion.

The tumor block used for diagnosis of GBM must be collected for each patient and sent for MGMT assessment (if not already done), biomarker and immunoscore analysis. The availability of these samples is mandatory for the baseline visit.

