## **3. OBJECTIVES OF THE STUDY**

### **3.1. Primary Objective**

To determine the safety and tolerability of avelumab 10mg/kg administered IV Q2weeks in patients receiving standard therapy for newly diagnosed GBM.

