### **4.2. Treatment Phases of the Study**

**Combination Phase:** Upon completion of the standard combination therapy of radiotherapy (total dose 60 Gy, administered as daily 2Gy fractions, 5 days/week or as per local standard) and temozolomide (75 mg/m^2/day p.o. qd) and a treatment break of no more than 21 days, the combination phase will start. Patients will receive temozolomide and avelumab for 6 cycles of 28 days each. During the 1st cycle Temozolomide will be given the first 5 days at a dose of 150mg/m^2/day p.o. In the next cycle, the temozolomide dose should be escalated to 200/mg/m^2 if permitted by the patient's hematological and non-hematological toxicity profile (as per NCI-CTC AE version 5). The temozolomide dose will be adjusted according to hematological and non-hematological toxicity as per temozolomide's product monograph (appendix 4). Avelumab will be administered on day 1 and day 15 of each cycle at a dose of 10mg/kg IV. Avelumab therapy will be withheld according to the occurrence and severity of avelumab emergent adverse events as per table 3. Patients will continue the

combination of temozolomide (150 – 200mg/m^2 per day PO X5 days Q28days) and avelumab (at 10mg/kg dose, IV on days 1 and 15 per cycle) until 6 cycles are completed or until the occurrence of a termination event.

**Monotherapy Phase:** Upon completion of the Combination Phase or upon stopping temozolomide because of temozolomide related toxicity/tolerability issues or patient choice, the patient will continue into the avelumab Monotherapy Phase. Avelumab 10mg/kg IV Q2weeks will be continued as monotherapy until the occurrence of a termination event defined as one of the following: 1) clinical evidence of neurological deterioration resulting in an ECOG score of at least 3 or more, unexplained by other comorbidities, unchanged by an increase in corticosteroid dose and sustained for at least two weeks or 2) treatment emergent adverse event (TEAE) of grade 3 or more or 3) withdrawal of patient consent.

Patients who experience irAE's may according to table 3 directives have their avelumab therapy suspended.

The use of Bevacizumab or re-irradiation will not be allowed in the study and will be considered as evidence of a termination event.

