## **5. ENDPOINTS**

### **5.1. Primary**

Safety and tolerability based on avelumab treatment emergent adverse events leading to permanent or transient discontinuation of avelumab

Treatment emergent adverse events of special interest will include those of autoimmune origin (irAE).

The adverse events will be graded according to the National Cancer Institute Common Terminology Criteria for Adverse Events, version 5.0

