### **9.3.4. Assessments at end of study**

An end of treatment study visit will occur when:

- 1) Grade 3 or higher avelumab related toxicity occurs
- 2) Evidence as per the iRANO criteria of tumor progression occurs and patient does not wish to continue treatment
- 3) Patient wishes for any reason to discontinue treatment or withdraw from the study. Clinical evidence of neurological deterioration resulting in an ECOG score

of at least 3 or more, unexplained by other comorbidities, unchanged by an increase in corticosteroid dose and sustained for at least two weeks.

A history, physical and neurological exam will be performed by a physician. Laboratory test as per schedule will be drawn. If any of the latter have already been performed to confirm the AE or tumor progression on the basis clinical neurological deterioration, then they need not be repeated.

A study specified gadolinium enhanced MRI or CT scan will be performed within 2 weeks of the end of study visit for all patients after 52 weeks.

Patients however who discontinue the study treatment on the basis of avelumab treatment related AE's or clinical evidence of tumor progression a study specified MRI or CT scan will be done at the discretion of the investigator.

Patients who prematurely discontinue study treatment will be encouraged to continue into the Extended Safety Follow-up phase of the study

Patients who not only end treatment but also withdraw from the study, for any reason, will be encouraged to have telephone follow ups every month in order to obtain survival information with regards to OS. Pathology samples will be obtained for repeat biomarker analysis if a second tumor surgery occurs

**NOTE:** Since the actual duration of pseudoprogression and the time for immunotherapies to become effective in patients with GBM are still unknowns patients will be allowed at the investigator and patient discretion to continue on study treatment after confirmation of radiographic progression unless there is significant drug toxicity Grade 3 or higher AE's unrelated to avelumab such as those secondary to intercurrent illness or temozolomide therapy do not constitute for the purpose of this study a reason to withhold avelumab therapy or withdraw the patient from the study.

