## **10. INVESTIGATIONAL MEDICINAL PRODUCT**

### **10.1. Dose and Schedule of Test Drug**

Avelumab is a fully human IgG1 antibody directed against PD-L1. Avelumab binds PD-L1 and blocks the interaction between PD-L1 and its receptors PD-1 and B7.1. This removes the suppressive effects of PD-L1 on anti-tumor CD8+ T cells, resulting in the restoration of cytotoxic T cell response.

Avelumab will be administered intravenously every 14 days starting the same day as the first day of the first 5 days po temozolomide treatment. Temozolomide's 28 days cycle will be repeated 6 times or until grade 3 or higher temozolomide related treatment AE's. Avelumab will be continued IV q14 days for 260 weeks or until grade 3 or higher avelumab treatment-related AE's occurs and independent of whether the patient continues or completes the 6 cycles of temozolomide.

Avelumab may be withheld temporarily in the case of irAE according to the irAE's algorythms (table 3)

Temozolomide dose may be adjusted or withheld according to the directives in the temozolomide's product monograph (appendix 4)

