### **11.4. Treatment Emergent Adverse Event (TEAE) Requiring Avelumab Discontinuation or Modifications**

The following TEAE's require permanent treatment discontinuation of avelumab:

- **Any Grade 4 TEAE require treatment discontinuation with avelumab** except for single laboratory values out of normal range that are unlikely related to study treatment as assessed by the Investigator, do not have any clinical correlate, and resolve within 7 days with adequate medical management
- **Any Grade 3 TEAE's require treatment discontinuation with avelumab except for any of the following:**
  - Transient ( $\leq$  6 hours) Grade 3 flu-like symptoms or fever, which is controlled with medical management
  - Transient ( $\leq$  24 hours) Grade 3 fatigue, local reactions, headache, nausea, emesis that resolves to Grade  $\leq$  1

- Single laboratory values out of normal range (excluding Grade  $\geq 3$  AST or ALT combined with  $\geq 2$  ULN total bilirubin) that are unlikely related to study treatment according to the Investigator, do not have any clinical correlate, and resolve to Grade  $\leq 1$  within 7 days with adequate medical management
- Change in ECOG PS to  $\geq 3$  that does not resolve to  $\leq 2$  within 14 days (infusions should not be given on the following cycle, if the ECOG PS is  $\geq 3$  on the day of Avelumab administration)

- **Any Grade 2 TEAE should be managed as follows:**

If a Grade 2 ADR resolves to Grade  $\leq 1$  by the last day of the current cycle, treatment may continue.

- If a Grade 2 TEAE does not resolve to Grade  $\leq 1$  by the last day of the current cycle, infusions should not be given on the following cycle. If at the end of the following cycle the event has not resolved to Grade 1, the subject should permanently discontinue treatment with avelumab. TEAE (except for hormone insufficiencies, that can be managed by replacement therapy; for these hormone insufficiencies, up to 2 subsequent doses may be omitted).
- Upon the second occurrence of the same Grade 2 TEAE (except for hormone insufficiencies that can be managed by replacement therapy) in the same subject, treatment with avelumab has to be permanently discontinued.
- Infusion-related reactions, hypersensitivity reactions (Grades 1 to 4), and tumor lysis syndrome should be handled according to guidelines provided.

The Management for Symptoms of Infusion-Related Reactions are listed in the table below:

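### The protocol contradicts itself on whether a Grade 3+ event unrelated to avelumab stops avelumab, and the endpoint wordings disagree on whether such a stop counts

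*SAP*

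**What the plan says.** The primary objective (protocol 3.1) is "To determine the safety and tolerability of avelumab 10mg/kg administered IV Q2weeks in patients receiving standard therapy for newly diagnosed GBM".

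The endpoint serving that objective appears in three forms:
- SAP 1.3.1, protocol 12.3.1 and the synopsis list of endpoints: "Safety and tolerability based on avelumab related adverse events leading to permanent or transient discontinuation of avelumab".
- Protocol 5.1: "Safety and tolerability based on avelumab treatment emergent adverse events leading to permanent or transient discontinuation of avelumab".
- The synopsis paragraph on statistical analysis refers to drug-related events leading to discontinuation. It does not say which drug.

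The rules for stopping avelumab fall into two groups.

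**No general attribution condition.** The termination event in the synopsis (Study Design) and in protocol 4.2 includes a "treatment emergent adverse event (TEAE) of grade 3 or more". Protocol 11.4 states: "Any Grade 3 TEAE's require treatment discontinuation with avelumab except for any of the following". It also stops avelumab for Grade 4 events, with one exception for isolated laboratory values.

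**Only for avelumab-related events.** Protocol 10.1 continues avelumab until a Grade 3 or higher event related to it, "independent of whether the patient continues or completes the 6 cycles of temozolomide". Protocol 9.3.4 lists avelumab-related Grade 3 or higher toxicity as the trigger for the end-of-treatment visit. Its note adds that "Grade 3 or higher AE's unrelated to avelumab such as those secondary to intercurrent illness or temozolomide therapy do not constitute" a reason to hold avelumab or to take the patient off study.

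**The concern.** The trial gives avelumab together with temozolomide for up to six cycles, so Grade 3 or higher events attributed only to temozolomide are foreseeable. The protocol plans for them: "upon stopping temozolomide because of temozolomide related toxicity/tolerability issues or patient choice, the patient will continue into the avelumab Monotherapy Phase" (4.2). For exactly these patients the two groups of rules give opposite instructions, one being to stop avelumab permanently and the other to carry on.

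Two things are at stake. The first is conduct: the same clinical event may end the investigational treatment in one patient and not in another. The second is the primary endpoint, which is built on discontinuations of avelumab. If a stop made under 11.4 for an unrelated event occurs, the three endpoint wordings do not agree on whether to count it.

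**Working it through.** **Step 1. The stopping rules side by side.**

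| Place in protocol | Grade 3+ event attributed only to temozolomide |
|---|---|
| Synopsis (Study Design) and 4.2, termination event | Avelumab stops |
| 11.4 | Avelumab stops permanently, unless a listed exception applies |
| 9.3.4, trigger list and note | Avelumab continues |
| 10.1 | Avelumab continues |

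Could 11.4 be meant to cover related events only? One of its exceptions is for single laboratory values that the investigator thinks unlikely to be related to study treatment, that have no clinical correlate and that resolve within 7 days. That exception would be unnecessary if unrelated events were already outside the rule. As written, unrelated events are in scope.

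**Step 2. One patient followed through.** Take a first Grade 3 non-haematological event, other than those exempted in Appendix 4 Table 9, attributed only to temozolomide and meeting no exception in 11.4. Table 9 calls for a one-level temozolomide reduction. (10.1 also mentions stopping temozolomide at Grade 3; that does not settle what happens to avelumab.) The contribution to the primary count is:

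| Endpoint wording | Avelumab continues (9.3.4, 10.1) | Avelumab stopped (11.4, termination event) |
|---|---|---|
| *avelumab related* (SAP 1.3.1, 12.3.1, synopsis endpoints) | 0 | 0 |
| *treatment emergent* (5.1) | 0 | 1 if read as timing only; 0 if read as caused by avelumab |
| *drug related* (synopsis, statistical analysis) | 0 | 1 if temozolomide is a drug in this sense; 0 if not |

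Under the SAP wording the count is the same in both columns, but the patient's treatment is not. Under the other two wordings the count can change as well.

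**Step 3. What one patient is worth.** The plan's own precision figure for a rate reproduces: 1.96 × √(0.5 × 0.5 / 30) = 0.179, stated as less than 18%. One reclassified patient moves the rate by 1/30 = 3.3 points. Five move it by 5/30 = 16.7 points, and six by 6/30 = 20.0 points, which exceeds that margin. For illustration, assume 3 patients counted under the SAP wording: 3/30 = 10.0% (exact 95% CI 2.1% to 26.5%). If three more were stopped under 11.4 and counted under 5.1, the rate would be 6/30 = 20.0% (7.7% to 38.6%).

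**Step 4. How many patients.** If a proportion *r* of patients has such an event, the expected number is 30 × *r*. The documents give no value for *r*. Over an assumed range of 5% to 40%, this is 30 × 0.05 = 1.5 to 30 × 0.40 = 12 patients. That is an upper figure for any given *r*, because some of these patients would also stop for an avelumab-related event. The 9.5% rate of Grade 3 or higher treatment-related events in protocol section 2 concerns avelumab-related events, so it does not inform *r*.

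**The case against.** The best defence is that the intention is clear. The note in 9.3.4 deals with the temozolomide case by name, 10.1 agrees with it, and a specific provision should prevail over a general one. Protocol 4.2 also speaks of avelumab-emergent events when describing holds, so *treatment emergent* in 5.1 and 11.4 may be loose wording for caused by avelumab. This stands as evidence of intent, and it sets the direction of the fix. It does not remove the contradiction: 11.4 is the section a site would consult when a toxicity occurs, it prescribes permanent discontinuation, and its laboratory exception points the other way.

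A reader might infer more, namely that the endpoint is wrong because it leaves out toxicity attributed to or managed through temozolomide. The documents do not support that. The objective is the safety of avelumab in patients on standard therapy, and an avelumab-related endpoint fits it. All adverse events are recorded (11.13) and attributed by drug (11.1.3). Temozolomide exposure and cycle completion are already needed for the exploratory analyses (5.3 and SAP 1.3.3).

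A reader might also express temozolomide shortfalls as a share of a full-dose total of 5 × 150 + 5 × 5 × 200 = 5750 mg/m². That denominator is a maximum in the absence of toxicity. Escalation to 200 mg/m² is conditional in 4.2, 10.3 and Appendix 4 Table 8, so six cycles at 150 mg/m² are within the protocol dose and are not lost treatment.

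**Conclusion.** The inconsistency is real and lies in the text: two sets of sections give opposite instructions for Grade 3 or higher events unrelated to avelumab, and three endpoint wordings treat the resulting stops differently. The consequence for an affected patient is permanent loss of avelumab or none. The consequence for the primary rate is 0 or 3.3 points per patient. The number of patients affected is unknown and could be zero. No tolerability threshold is set, and the efficacy rule and sample size are untouched, so no formal decision changes.

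The conclusion rests on reading 11.4 and the termination event as written and *treatment emergent* in its usual sense of timing. If the sponsor meant caused by avelumab throughout, the remedy is the same: say so.

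**What to change.** 1. In 11.4 and in the termination event (synopsis and 4.2), limit the Grade 3 and Grade 4 stopping rules to treatment-emergent events assessed as related to avelumab, including those where a relation cannot be excluded. State that *yes* and *probably* in 11.1.3 both count as related. Keep 9.3.4 and 10.1, and align the toxicity item in 6.2, which also has no attribution condition. If the sponsor prefers the stricter rule, 9.3.4 and 10.1 must be changed instead.
2. Use the SAP 1.3.1 endpoint wording in the synopsis (both places), 5.1, 12.3.1 and the SAP. Make the matching change in the sentence of 5.1 on events of special interest.
3. Optional: because attribution between two concurrent drugs is uncertain, also report the number of patients with any Grade 3 or higher treatment-emergent event regardless of attribution, with an exact 95% CI. Note beside it that, without a control arm, it mixes avelumab, temozolomide and tumour effects. At n = 30 the interval is wide: 0/30 gives 0% to 11.6%, and 15/30 gives 31.3% to 68.7%.

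The cost is a wording amendment handled under protocol 15.2, possibly with a matching change to the consent form, and one table if the option is taken. Attribution by drug is already recorded, so no new data, patients or alpha are needed. The price of the narrower rule is more reliance on the investigator's attribution, which is why events with a relation that cannot be excluded should still stop avelumab.

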1.3.2. Secondary Endpoints

Based on the results of Stupp *et al* (2005) (3), if avelumab had no effect then we would expect to see one-year overall survival and progression-free survival rates of 60% and 27%, respectively. We will conclude that we have preliminary evidence of benefit if either of our observed rates is significantly better based on a one-sided t-test at the 0.2 level of significance. With our projected sample of 30, this corresponds to concluding benefit if at least 21 patients survive to one-year or if at least 11 have survived without progression of disease.

Radiological tumor response will be graded according to the immunotherapy Response Assessment for Neuro-Oncology (iRANO)

Progression of Disease (PD) will be defined as a $\geq 25\%$ increase on the 12 month MRI or CT scan in the sum of the product of the biperpendicular diameters of enhancing disease; or new lesions; or substantial worsened T2/FLAIR; or significant clinical neurological decline unexplained by a change in medication or concurrent comorbidities. The SPD is the sum of the products of biperpendicular diameters of the measurable enhancing lesions (max 5 lesions).

Complete Response (CR) will be defined as the disappearance on the month 12 MRI or CT scan of all enhancing disease, no new lesions, with stable or improved T2/FLAIR; no more than physiological steroids; clinically stable or improved

Partial Response (PR) will be defined as a $\geq 50\%$ decrease on the month 12 MRI or CT scan in the sum of the product of the biperpendicular diameters of enhancing disease, no new lesions, stable or improved T2/FLAIR, stable (>2 months) or decreased steroid dose, clinically stable or improved

Stable Disease (SD) will be defined at 12 months when a patient do not qualify for complete response, partial response, or progressive disease, stable or improved T2/FLAIR; stable (>2 months) or decreased steroid dose, clinically stable or improved

Overall survival (OS) will be defined as the time from baseline to the date of death from any cause.

Objective Response Rate (ORR) will be defined the number of patients with either CR or PR divided by the total number of patients.

Progression Free Survival (PFS) will be defined as the time from baseline to documented PD or death from any cause.

Results will be stratified according to MGMT status, baseline age (>50 yrs), baseline Karnofsky performance score (score of 100), radical tumor resection vs biopsy, primary versus secondary GBM,

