#### IV. STUDY FLOW CHART

**The Monotherapy phase will continue until a termination event**

## **PART I: STUDY DESIGN AND CONDUCT**

### **1. BACKGROUND AND RATIONALE**

#### **1.1. Background**

##### **1.1.1 Glioblastoma**

Glioblastoma Multiforme (GBM) is the most common malignant primary brain tumor. It represents a WHO grade 4 glioma. It has an annual incidence of 3-5/100,000. It shows a slight predominance for males and a peak incidence between the fifth and sixth decades but can occur at any age. (1) Without treatment the 1 and 5 year survival is 29% and 3 % respectively (2).

Despite standard therapy of maximum resection followed by concurrent radiotherapy (60Gy) and temozolamide followed by 6, 5day, monthly cycles of temozolomide (TMZ) the median survival is 15 months and the 2-year survival, 27% (3). Recurrence of GBM usually occurs within a few months.

Recent phase 3 trials looking at escalating the radiotherapy dose beyond the 60Gy, increasing the dose of TMZ as adjuvant or maintenance therapy (8) or the addition of cilengitide (9) or bevacizumab (10) did not improve overall survival (OS).

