**Progression of Disease (PD) based on radiographic parameters:**

Patients with stable clinical neurological status with stable dexamethasone dose of 12mg/day or less and evidence of radiological progression defined as a  $\geq 25\%$  increase in the sum of the biperpendicular diameters of enhancing disease; or substantial worsened T2/FLAIR; or new lesions on gadolinium enhanced MRI or CT scan done less than 6 months from baseline will require confirmation on a repeat imaging done 3 months later. The first MRI or CT scan showing progression will act as the new baseline and if progression is confirmed the date of progression will be backdated to the new baseline MRI or CT scan where the progression was first noted.

If the first radiological evidence of progression or new lesions occurs 6 months or more from baseline then no confirmatory imaging will be required.

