For index lesions the Sum of the Product of the biperpendicular Diameters of the measurable enhancing lesions (SPD) will be recorded and used for comparison. An increase in the lesion SPD noted prior to month 6 will require confirmation 3 months later using the last MRI or CT scan as baseline comparison. The 12 months MRI or CT scan will be compared to baseline.

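### The 60% OS and 27% PFS no-effect rates are not shown to match this trial's clock, entry selection or progression rule, and the either-endpoint rule built on them has little slack: its false-positive rate is about 0.27 even at those rates

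*SAP*

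**What the plan says.** SAP 1.3.2 (same text in Protocol 12.3.2) states that "if avelumab had no effect then we would expect to see one-year overall survival and progression-free survival rates of 60% and 27%, respectively", citing reference 3. It then concludes preliminary benefit if either rate is significantly better at one-sided 0.2, which it translates into at least 21 of 30 alive, or at least 11 of 30 alive and progression-free, at one year. The reference list and Protocol 1.1.1 identify reference 3 as a 2005 study of radiotherapy with concomitant and adjuvant temozolomide.

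This trial's clock is different in kind: "Overall survival (OS) will be defined as the time from baseline to the date of death from any cause", and PFS has the same start. Protocol 4.1 puts entry within 3 weeks of the end of chemoradiation.

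On progression, Protocol 5.2 says that radiographic worsening "done less than 6 months from baseline will require confirmation on a repeat imaging done 3 months later", and "if progression is confirmed the date of progression will be backdated to the new baseline MRI or CT scan". For later scans, "If the first radiological evidence of progression or new lesions occurs 6 months or more from baseline then no confirmatory imaging will be required". Protocol 9.3.5 adds that local scans are used after month 6 to look for progression. The SAP's own PD text instead refers to an "increase on the 12 month MRI or CT scan in the sum of the product of the biperpendicular diameters of enhancing disease", and Protocol 9.3.5 says "The 12 months MRI or CT scan will be compared to baseline".

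**The concern.** In a single-arm trial the no-effect rate is the comparator. If reference 3 measured survival from a different time zero, in differently selected patients, or with a different progression rule, then 21 or 11 of 30 could be reached, or missed, for reasons unrelated to avelumab. Neither document gives that study's time zero, entry criteria or progression rule, so the match cannot be checked. iRANO, by Protocol 2.1, was published in November 2015, so a 2005 study cannot have applied that publication.

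At stake is the one inferential statement in the plan: the claim of preliminary benefit. The primary safety objective is unaffected.

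**Working it through.** **1. Reproduce the cut-offs.** Inputs from SAP 1.1 and 1.3.2: n = 30, p0 = 0.60 and 0.27, one-sided 0.2. The error rate of a count rule is exact binomial, P(X ≥ r) = Σ C(30,k) p^k (1−p)^(30−k), summed over k = r to 30.

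| Endpoint | Count | Exact p | t-test p |
|---|---|---|---|
| OS, 60% | 20 | 0.292 | 0.226 |
| OS, 60% | 21 | 0.176 | 0.125 |
| PFS, 27% | 10 | 0.276 | 0.238 |
| PFS, 27% | 11 | 0.161 | 0.145 |

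By either method 21 and 11 are the smallest significant counts. The plan's figures are right for its stated rates.

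**2. Slack, each endpoint alone.** Solving P(X ≥ 21) = 0.2 gives p = 60.79%; P(X ≥ 11) = 0.2 gives p = 28.16%. The slack is 0.79 and 1.16 percentage points, or 0.0079 × 30 = 0.24 and 0.0116 × 30 = 0.35 of a patient. Over a range of true no-effect rates:
- OS 55 / 60 / 65%: 0.07 / 0.18 / 0.36.
- PFS 20 / 25 / 27 / 30 / 35%: 0.03 / 0.11 / 0.16 / 0.27 / 0.49.

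**3. The rule the SAP uses (either endpoint).** Progression-free patients are a subset of survivors. Assume that patients are independent and that each survivor is progression-free with probability p_PFS / p_OS. Then

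P(either) = P(X ≥ 21) + Σ (x = 11 to 20) P(X = x) · P(Y ≥ 11), with Y ~ Binomial(x, p_PFS / p_OS).

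At 60%/27%: 0.176 + 0.093 = 0.269. (If the endpoints were independent: 1 − 0.824 × 0.839 = 0.309.) The same formula over the range:

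| OS rate | PFS 20% | 25% | 27% | 30% | 35% |
|---|---|---|---|---|---|
| 55% | 0.09 | 0.15 | 0.19 | 0.29 | 0.50 |
| 60% | 0.19 | 0.23 | 0.27 | 0.34 | 0.52 |
| 65% | 0.36 | 0.39 | 0.41 | 0.46 | 0.59 |

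**4. Can the direction be inferred?**
- *Clock, OS.* Assume, since the documents do not say, that reference 3 counts from the start of radiotherapy. Six weeks of radiotherapy (Protocol 10.4) plus 0 to 3 weeks gives d = 6 to 9 weeks. A Weibull curve through 60% at 12 months and 27% at 24 months (median 15.0 months, matching Protocol 1.1.1) gives S(12+d)/S(d) = 56.8% to 55.6%. The level of the 21 cut-off alone is then 0.10 to 0.08. On this assumption the clock lowers the OS rate.
- *Selection.* Entry requires Karnofsky 70 or more, limited dexamethasone and adequate laboratory values (Protocol 7.1). Selecting fit patients after chemoradiation may raise the rate. The documents give no figure.
- *Progression rule.* Suppose a share f of benchmark patients counted as progressed only through early worsening that would not be confirmed, and their one-year PFS is otherwise r (both assumed). The no-effect PFS is 27% + f·r, and the single-endpoint level passes 0.2 once f·r exceeds 1.16 points. With f = 10%, r = 10% it is 28.0% and the level 0.19; with f = 20%, r = 10% it is 29.0% and 0.23. The pseudoprogression figure above 20% in Protocol 1.1.1 does not supply f. Protocol 8.2 (bevacizumab, re-irradiation) and 8.4 (certain dexamethasone use after month 3) count extra events as progression and push the other way.

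The forces oppose each other and none can be sized from the documents.

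**5. The rule behind the 11-of-30 count.** Take a clinically stable patient with a 25% increase at month 8 that has receded below 25% by month 12, without new lesions or worse T2/FLAIR. Under Protocol 5.2 and 9.3.5 this patient has progressed, with no confirmation needed. Under the SAP's PD text, read literally, the 12-month scan decides, and the patient has not.

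**The case against.** Uncertainty about a historical control comes with any single-arm trial, and the plan hedges: a convenience sample, a descriptive focus (SAP 1.1), a safety primary endpoint and only preliminary evidence claimed. That stands, and it limits the seriousness. It does not remove a prespecified level with two cut-offs, whose results cannot be read without knowing what the comparator measured.

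A second objection is that the Protocol already settles the progression rule. In Protocol 5.2 the any-time rule falls under conduct during the study, the 12-month wording falls under week 260 or end of study, and 9.3.5 uses local scans after month 6. This largely stands: the month-8 patient counts as progressed under the Protocol. What remains is that the SAP carries only the 12-month wording.

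Stronger readings are tempting but unsupported:
- *The rates are too low, so the rule is too lenient.* Step 4 shows effects in both directions and no way to net them.
- *The OS bar is too strict and should fall to 20.* This rests on an assumed time zero and ignores entry selection. With OS at 56.8% to 55.6% and PFS at 27%, the either-rule is at 0.21 to 0.20 with a cut-off of 21, and 0.27 to 0.25 with 20. If the true OS rate is 60%, P(X ≥ 20) alone is 0.29.
- *The cut-offs were miscalculated.* They were not.

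**Conclusion.** The concern holds as a minor one. The documents do not show that 60% and 27% describe what this trial's patients would do without avelumab on this trial's clock and progression rule, and the direction of any net error is not established. The practical consequence is the thin margin: less than half a patient per endpoint before a single cut-off exceeds 0.2, and an either-rule error of about 0.27 at the plan's own rates, running from about 0.09 (55%/20%) to 0.59 (65%/35%). The either-rule figures assume independent patients and a common chance of being progression-free among survivors; the single-endpoint limits are exact for 30 evaluable patients. Separately, the SAP's 12-month PD wording and the Protocol's any-time rule must be reconciled before the 11-of-30 count has one meaning.

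**What to change.** 1. In SAP 1.3.2, and likewise in Protocol 12.3.2, report the false-positive rate of each cut-off and of the either-rule over OS no-effect rates of 55% to 65% and PFS rates of 20% to 35%. The figures in steps 2 and 3 would serve.
2. Word a positive result as exceeding the historical rate, and state the differences in clock, entry selection and progression rule as limits on that statement.
3. State that the one-year PFS count uses the any-time progression rule of Protocol 5.2 and 9.3.5, and reconcile the 12-month PD text in SAP 1.3.2 with it.

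The OS cut-off should not be changed on a clock-only calculation, and a second PFS definition is not needed. The cost is a short table, a few sentences, and openly stating a less favourable error rate than 0.2. The wording is best settled before the first interim look, when 10 patients have reached week 52 or the end-of-study visit (SAP 1.2).
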